**INCLUSION / EXCLUSION CRITERIA:** Patients with spino-cerebellar ataxia, Friedreich's ataxia, multisystem atrophy, sporadic ataxia in adult onset will be included. Patients affected by: i) cerebrovascular diseases, hydrocephalus, expansive intracranial processes ii) significant medical problems (eg diabetes and arterial hypertension poorly controlled; cancer in the past 5 years) will be excluded iii) major depressive disorders, bipolar disorders, schizophrenia, abuse of substances, mental retardation according to DSM-IV criteria) implanted metal objects or history of epilepsy. Patients should not suspend any ongoing therapy.

Presidio Ospedaliero  
di Brescia

Regione  
Lombardia  
ASST Spedali Civili

Università  
degli Studi  
di Brescia

CLINICA NEUROLOGICA - UNIVERSITA' DEGLI STUDI DI BRESCIA  
UO Neurologia 2 - AZIENDA SOCIO SANITARIA TERRITORIALE degli SPEDALI CIVILI DI BRESCIA  
Direttore: [name]

**STUDY DESIGN:** this is a randomized, double-blind, non-pharmacologic, placebo-controlled clinical trial, since neither patients nor those who will administer the evaluation tests will be aware of the type of treatment carried out, real-tDCS or sham (anodic tDCS: placebo tDCS = 1: 1) with cerebellar tDCS 5 days a week for 2 consecutive weeks in 40 patients with neurodegenerative ataxia.

A randomized stratification by type of pathology will be implemented, so as to balance the patients with the same pathology between the two groups (real and sham). Subsequently, a randomization in blocks will be implemented, in order to balance the quantitative asymmetry of the patients assigned to the two groups, guaranteeing a similar number of patients enrolled in the two groups, even if the trial should be interrupted early.

Patients with spinocerebellar ataxia, Friedreich's ataxia, multisystem atrophy, sporadic ataxia in adult onset will be included. Each patient will undergo a clinical evaluation (cognitive performance, quality of life and performance of motor coordination and balance), evaluation of CBI connectivity by transcranial magnetic stimulation at baseline (T0), after 2 weeks of treatment with tDCS (T1) and follow -up to 3 months (T2).

An open phase will follow and all patients will receive an anodic tDCS stimulation at the cerebellar and cathodic levels at the spinal level (5 days / week for 2 weeks) and will receive the same standardized evaluation after the 2-week treatment (T3), at the follow- up to 3 months (T4) and 6-month follow-up (T5).

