## **END POINTS:**

### ***Primary Outcome Measures:***

1. Change in the International Cooperative Ataxia Rating Scale (ICARS) Score (Baseline – 2 Weeks).
2. Change in the Scale for the Assessment and Rating of Ataxia (SARA) Score (Baseline – 2 Weeks).
3. Change in the Cerebellar cognitive affective syndrome (CCAS) Scale (Baseline – 2 Weeks).

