### ***Secondary Outcome Measures:***

4. Change in the International Cooperative Ataxia Rating Scale (ICARS) Score (Baseline - 2 weeks - 3 month - 6 months - 9 months).
5. Change in the Scale for the Assessment and Rating of Ataxia (SARA) Score (Baseline - 2 weeks - 3 month - 6 months - 9 months).
6. Change in the Cerebellar cognitive affective syndrome (CCAS) Scale (Baseline - 2 weeks - 3 month - 6 months - 9 months).

7. Change in Cerebellar Brain Inhibition (CBI) Measurements (Baseline - 2 weeks - 3 month - 6 months - 9 months).
8. Change in the Short-Form Health Survey 36 (SF36) Score (Baseline - 2 weeks - 3 month - 6 months - 9 months).

**STATISTICAL PLAN:** we will use parametric analyzes (t tests) to compare the demographic variables (age and education) of the two groups at the baseline. A  $P < 0.05$  will be considered significant. To evaluate the effect of the stimulation protocol by means of tDCS on cognitive performances, of motor coordination and balance and quality of life, at T 2-3-4-5 we will use a mixed-model ANOVA.

We performed a "power analysis" to estimate the sample size, based on some previously published studies (Benussi A, Brain Stimul, 2017) using methods similar to those applied in the study in question. The "effect size"  $f(V)$  was calculated by direct method. Taking into account the aforementioned studies an effect size equal to a partial  $\eta^2$  of 0.037, equal to an "effect size"  $f(V)$  of 0.195 and, considering alpha = 0.05 and the power  $(1-\beta) = 0.80$ , the expected sample size is 54 subjects using a repeated measures ANOVA study. The proposed sample size of 60 subjects should be adequate to achieve the main objective of the study.

**ETHICAL CONSIDERATIONS (RISK-BENEFIT):** tDCS is a non-invasive, low-cost and easy-to-implement method which is having an increasing diffusion and an increasingly numerous spectrum of potential therapeutic applications such as, for example, post-stroke rehabilitation, depression and pain, already consolidated. Recently its efficacy in modulating cerebellar excitability in humans (Galea 2009) has been demonstrated with favorable effect of cerebellar anodic stimulation by tDCS on motor learning and walking (Jayaram 2012).

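### The sample size of 54 does not follow from its stated effect size: on the f(V) scale, 54 patients give 29% to 68% power, not 80%

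*Combined protocol and SAP*

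**What the plan says.** The power paragraph under STATISTICAL PLAN takes a partial eta-squared of 0.037 from earlier published work, sets it equal to an f(V) "of 0.195 and, considering alpha = 0.05 and the power" (0.80), and concludes that "the expected sample size is 54 subjects using a repeated measures ANOVA study". It then proposes 60 subjects as adequate. It does not give the term tested, the number of measurements, the correlation among them or a sphericity correction.

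For the analysis, the same section says "we will use a mixed-model ANOVA" and refers to T2 to T5. Under END POINTS, all three primary outcomes (ICARS, SARA, CCAS) are changes from baseline to 2 weeks. STUDY DESIGN describes two arms allocated 1:1 and visits T0 to T5, and puts the trial "in 40 patients with neurodegenerative ataxia". It adds that after T2 "An open phase will follow and all patients will receive an anodic tDCS stimulation".

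**The concern.** This paragraph is the only justification of the sample size. The effect is given on a named scale, f(V), and tied to partial eta-squared. On that scale the gain from repeated measurement is already absorbed into the effect, so an effect this small should need well over 54 patients. If so, the stated 80% is wrong for the effect quoted.

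Real and sham stimulation are compared only at T0, T1 and T2, because everyone then receives active stimulation. Two or three visits are therefore what matters for efficacy, and power on the f(V) scale is lowest there. A reader who trusts 80% would take a null result as stronger evidence against an effect than it is.

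**Working it through.** **Inputs from the documents.** f(V) = 0.195, partial eta-squared 0.037, alpha 0.05, target power 0.80 and N = 54 or 60 (STATISTICAL PLAN); two groups 1:1, visits T0 to T5 and N = 40 (STUDY DESIGN). The number of visits m is not stated for the power calculation, so 2 to 6 are all tried. Sphericity is assumed, which favours the plan.

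**Step 1: do the two effect sizes agree?** f = sqrt(0.037/(1 − 0.037)) = 0.196, so yes, to rounding.

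**Step 2: power on the stated scale.** For the group-by-time term, the noncentral F has df1 = m − 1, df2 = (N − 2)(m − 1) and lambda = f²·N·(m − 1). With m = 2 and N = 54, lambda = 0.195² × 54 = 2.05 on 1 and 52 df, which gives 29.0%.

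| Visits m | N = 40 | N = 54 | N = 60 | N for 80% |
|---|---|---|---|---|
| 2 | 22.5% | 29.0% | 31.8% | 210 |
| 3 | 31.4% | 41.5% | 45.6% | 130 |
| 4 | 39.3% | 51.9% | 56.8% | 98 |
| 5 | 46.3% | 60.6% | 66.0% | 80 |
| 6 | 52.6% | 68.0% | 73.4% | 70 |

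**Step 3: do variants on this scale rescue 54?**
- Lambda with N − 2 in place of N: 28.1% (m = 2) to 66.1% (m = 6).
- f = 0.196 in place of 0.195: 29.3% to 68.5%.
- Main effect of time: the same figures as in the table, to within rounding.
- Between-group test, lambda = f²·N: 29.0%.
- Multivariate test, lambda = f²·N: 29%, 22%, 18%, 16% and 15% for m = 2 to 6.
- Sphericity epsilon 0.75: 58.6% at m = 6.
- Alpha 0.10: 41.0% (m = 2) to 78.6% (m = 6).

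None reaches 80%.

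**Step 4: what does reproduce 54?** Treat 0.195 as a classical f and supply a correlation rho: lambda = f²·N·m/(1 − rho). With m = 2, rho = 0.5 and N = 54, lambda = 0.038025 × 54 × 2/0.5 = 8.21 and power is 80.3%; N = 52 gives 78.8%. So 54 is the smallest even N here. The same holds for the other pairs below. The implied interaction effect is f² = 0.195²·m/((m − 1)(1 − rho)); for m = 2 and rho = 0.5 this is 0.1521, and 0.1521/1.1521 = 0.132.

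| m | rho giving N = 54 | Implied partial eta-squared, group by time |
|---|---|---|
| 2 | 0.50–0.515 | 0.132–0.136 |
| 3 | 0.38–0.40 | 0.084–0.087 |
| 4 | 0.27–0.29 | 0.065–0.067 |
| 5 | 0.16–0.19 | 0.054–0.055 |
| 6 | 0.06–0.095 | 0.046–0.048 |

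Every implied interaction effect exceeds 0.037. A classical-f between-group test with m = 4 and rho = 0 also returns 54. Several settings fit, so the one actually used cannot be inferred.

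**Step 5: sensitivity to the missing correlation.** With classical f and m = 2, N for 80% is 76 at rho 0.3, 54 at 0.5 and 34 at 0.7.

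**Step 6: detectable effect for the primary comparison.** For a two-group comparison of T0–T1 change, two-sided 5%, 80% power: 0.91 SD of change at N = 40 (partial eta-squared 0.17), 0.78 SD at 54 (0.13) and 0.74 SD at 60 (0.12).

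**The case against.** The strongest defence is that 54 is not arbitrary. Two groups, two measurements and a correlation of 0.5 give exactly 54 if 0.195 is a classical f, and two measurements match the primary endpoints. On that reading 60 patients have 84% power. The likeliest explanation would then be unreported inputs and perhaps a mislabelled effect size, rather than a failed calculation. This is a fair account of how 54 may have arisen. It does not make 54 follow from what is written: the plan names f(V), states no correlation, and quotes 0.037 where the two-visit interaction implied by that reading is about 0.13.

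A second objection is that the figures for three or more visits depend on the univariate test. That is so, but the multivariate version gives lower power, and the two-visit 29% is common to both.

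A third is that the documents do not say whether 0.037 is an interaction, time or group effect, or from what design it comes. This stands. The true shortfall cannot be determined, and the 29% for the primary comparison is conditional on 0.037 being its interaction effect. What is unconditional is that the labelled inputs do not produce 54.

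Finally, the conflict between 40 and 60 patients is a separate defect. It does not make this one worse, but the restated figure cannot be written until it is settled.

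**Conclusion.** The concern holds. With f(V) = 0.195 and alpha 0.05, 54 patients give 29% power with two visits and 68% with six, under sphericity; no visit count in the trial reaches 80%. For the visits at which real and sham can be compared, power is 29% with two and 42% with three. Reaching 54 requires another effect-size convention and an undisclosed correlation. For the group-by-time test, that means powering for a larger interaction than the one quoted, so if 0.037 is the interaction effect, the correlation has been counted twice.

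If 0.037 is the interaction for the T0–T1 comparison, an effect of that size would be missed about 70% of the time at 54 or 60 patients (71% and 68%) and 78% of the time at 40. On the favourable classical-f reading, over the group-by-time settings that return 54, power is 65–69% at 40 patients and 84–86% at 60. So no setting that reproduces 54 supports 80% with the number given under STUDY DESIGN.

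**What to change.** Rewrite the power paragraph.

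1. Stop describing 54 or 60 as giving 80% power for a partial eta-squared of 0.037.
2. State the outcome scale, the term tested, the number of visits, the assumed correlation, the sphericity assumption, and whether 0.195 is f(V) or a classical f.
3. Reconcile the 40 patients under STUDY DESIGN with the 60 under STATISTICAL PLAN.
4. Restate the figure for the primary comparison, the group difference in T0–T1 change. Either recompute power from the inputs in item 2, or give the detectable effect, which does not depend on what 0.037 refers to. Possible wording: *With 60 [40] patients allocated 1:1, a two-sided 5% test has 80% power, for each primary outcome taken singly, without adjustment for multiple outcomes and before dropout, to detect a difference of 0.74 [0.91] SD of change (partial eta-squared 0.12 [0.17]).*

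The cost is one paragraph and a less favourable stated figure. The correction itself requires no extra patients.

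### On the f(V) scale the protocol names, the planning effect gives about 29% power for the 2-week contrast at 54 patients, not 80%; the stated 54 needs a different effect-size convention and a correlation that the plan does not state

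*Combined protocol and SAP*

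**What the plan says.** The power paragraph in the STATISTICAL PLAN bases the effect on previously published studies. It gives partial eta-squared 0.037, equates this to an f(V) of 0.195, and says that the effect size "was calculated by direct method". With alpha 0.05 and power 0.80 it states that "the expected sample size is 54 subjects using a repeated measures ANOVA study", and then: "The proposed sample size of 60 subjects should be adequate to achieve the main objective of the study".

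The paragraph does not say which term was powered (group, time or their interaction), how many measurements were assumed, or what correlation between them was used.

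Elsewhere, END POINTS makes all three primary outcomes changes from baseline to 2 weeks, for example "Change in the Scale for the Assessment and Rating of Ataxia (SARA) Score (Baseline – 2 Weeks". STUDY DESIGN gives two arms at "anodic tDCS: placebo tDCS = 1: 1" and plans the trial "in 40 patients with neurodegenerative ataxia", against the 60 in the power paragraph.

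**The concern.** A partial eta-squared is the effect sum of squares divided by effect plus error for the term being tested. For a within-patient term, that error already reflects how strongly a patient's visits correlate. The f(V) derived from it therefore leaves no further gain from correlation. On this scale 0.037 is a modest effect, and 54 patients looks far too few for 80% power on a two-visit contrast.

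At stake is how a null result would be read. A reader who accepts 80% power would take it as evidence against an effect of the planned size. If the label f(V) is meant literally, the trial has less than one chance in three of detecting that effect at the primary time point.

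**Working it through.** **Inputs.** Partial eta-squared 0.037, f(V) 0.195, alpha 0.05, power 0.80, N = 54 and 60 (STATISTICAL PLAN); N = 40, two groups, 1:1 (STUDY DESIGN); m = 2 visits for the primary contrast (Primary Outcome Measures). The correlation rho and the m used by the sponsor are not stated, so ranges are shown.

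**Conversion.** f = sqrt(0.037/0.963) = 0.196, against 0.195 stated. This is rounding.

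**Reproducing 54.** The average-f formula for the interaction is lambda = f² × N × m/(1 − rho), with df1 = m − 1 and df2 = (N − 2)(m − 1). With f = 0.195, m = 2 and rho = 0.5 (assumed):
- N = 54: lambda = 0.038025 × 54 × 2/0.5 = 8.21, power 0.803
- N = 52: power 0.788

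So 54 is reproduced. Other pairs also give 54 when N is kept even: m = 3 with rho 0.38 to 0.40, m = 4 with 0.27 to 0.29, m = 5 with 0.16 to 0.19, m = 6 with 0.06 to 0.09. The result is sensitive to rho. At m = 2, the N required is 106 at rho 0, 75 at 0.3, 64 at 0.4, 44 at 0.6 and 33 at 0.7.

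**The effect as labelled.** Here lambda = f² × N × (m − 1), with the same degrees of freedom. For m = 2 and N = 54, lambda = 0.038025 × 54 = 2.05. This is the t test on change with d = 2f = 0.39 SD of change.

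Power at m = 2 (the lower value uses N − 2 in place of N):

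| N | Power |
|---|---|
| 40 | 0.22–0.23 |
| 54 | 0.28–0.29 |
| 60 | 0.31–0.32 |

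80% power requires N = 209 (211 with N − 2).

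More visits, with 0.195 carried unchanged:

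| m | N = 54 | N = 60 |
|---|---|---|
| 2 | 0.29 | 0.32 |
| 3 | 0.41 | 0.46 |
| 4 | 0.52 | 0.57 |
| 5 | 0.61 | 0.66 |
| 6 | 0.68 | 0.73 |

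These are the favourable values. With lambda = f² × N, or the MANOVA form, power at N = 54 falls from 0.29 at two visits to about 0.15 at six.

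**Effect implied by the average-f route.** Converted to the partial eta-squared scale, f² becomes f² × m/[(1 − rho)(m − 1)].
- m = 2, rho 0.5: 0.038025 × 4 = 0.152; partial eta-squared = 0.152/1.152 = 0.13; d = 2 × sqrt(0.152) = 0.78
- m = 3, rho 0.4: 0.038025 × 3/(0.6 × 2) = 0.095; partial eta-squared 0.09
- m = 6, rho 0.07: 0.038025 × 6/(0.93 × 5) = 0.049; partial eta-squared 0.05

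Each exceeds 0.037.

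**Effect detectable with 80% power, m = 2.** With d = sqrt(4 × lambda/N), where lambda is the value that gives 80% power: 0.91, 0.78 and 0.74 SD of change at N = 40, 54 and 60. The corresponding partial eta-squared, (d/2)²/[1 + (d/2)²], is 0.17, 0.13 and 0.12.

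**The case against.** The strongest reply is that 54 can be recovered exactly. A standard repeated-measures formula with two groups, two visits and rho 0.5 returns it, and two visits is the primary contrast. On that reading 54 gives 0.80 and 60 gives 0.84. A reader might therefore infer from the low power figures that the sponsor made an arithmetic error, or that the planning effect cannot give 80% power with 54 patients under any method. The documents support neither inference.

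It would also go too far to say that the sponsor assumed rho 0.5 with two visits, or planned on partial eta-squared 0.13. Several visit and correlation pairs give 54, with implied values from about 0.05 to 0.13, and the plan discloses none of these inputs.

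Two further cautions stand. The term to which 0.037 belongs is not named, so applying it to the 2-week interaction is an assumption. The figures for more than three visits are only a bound: T3 to T5 follow an open phase in which every patient receives stimulation, so six visits are not one randomized comparison.

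The label is not rescued by this reply. The protocol calls the effect f(V) and equates it to a partial eta-squared. The formula that yields 54 takes an effect not yet adjusted for correlation. If average-f was meant, the label is wrong and the sample size rests on an undisclosed correlation; with two visits and rho 0.5, the 40 patients in STUDY DESIGN would have power 0.67.

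**Conclusion.** The concern holds in conditional form. Taken as labelled and applied to the group-by-time term, the planning effect gives roughly 29% power at 54 and 32% at 60 for the 2-week contrast. None of the f(V) conventions tried reaches 0.80 at either size with 2 to 6 visits. Of the formulas tried, those that reproduce 54 treat 0.195 as an average-f with an unstated correlation.

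The most likely explanation is a mismatch of effect-size scale. It is inferred from the numerical match, since the plan states no convention. The stated 80% does not follow from the effect as the protocol describes it, and no reader can verify it from the inputs given. The difference between 40 and 60 patients is a separate inconsistency; it matters here because the power must be restated for the number actually to be enrolled.

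**What to change.** Keep enrolment as planned and rewrite the power paragraph:

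1. Name the tested term (group-by-time, baseline to T1), the number of visits, the correlation between them and the effect-size convention.
2. Then either report the power at partial eta-squared 0.037 for the N to be enrolled, or state the effect detectable with 80% power: about 0.91, 0.78 or 0.74 SD of change at N = 40, 54 or 60.
3. Remove the statement that 60 is adequate at f(V) 0.195, unless the sponsor shows that 0.195 is an average-f and justifies the correlation used with it.

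The cost is one paragraph and no extra patients. The downside is that the stated power becomes less favourable.

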#### CLINICA NEUROLOGICA - UNIVERSITA' DEGLI STUDI DI BRESCIA

UO Neurologia 2 - AZIENDA SOCIO SANITARIA TERRITORIALE degli SPEDALI CIVILI DI BRESCIA  
Direttore: [name]

Regarding the TMS method, it is a non-invasive brain stimulation that allows the study of neurophysiological parameters that can provide information on the pathophysiological mechanisms involved in neurodegenerative diseases.

Literature data show that the application of the method according to the current safety guidelines has little relevant side effects: a certain number of subjects participating in TMS experiments (up to 20%) suffer headaches or back pain, due to probably due to excessive muscle tension and a rigid position of the head and / or neck during the application of the TMS. These effects are temporary and in most cases do not require any treatment.

Since the TMS produces a magnetic field, people with fixed electrical stimulators (for example, cardiac stimulators, nerve stimulators, auditory implants) that would not work or would be damaged by the magnetic field cannot participate in the study. Examination is also excluded for people with particular metallic foreign bodies (such as splinters, some prostheses, screws and nails) that could move if placed inside the magnetic field. Since the effects of TMS on the developing fetus are not known, pregnant women cannot participate in the study.

**DETECTION OF ADVERSE EVENTS:** The Principal Investigator will promptly communicate to the Provincial Ethics Committee of the Province of Brescia any adverse event induced by the method.

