We therefore hypothesize that tDCS may have a positive effect on the performance of motor coordination and balance in patients with Spinocerebellar Atrophy, a group of neurodegenerative pathologies characterized by slowly progressive ataxia of walking, posture and limbs, associated with dysarthria and / or alteration of oculomotor, for which currently no treatments are available.

Literature data show that the application of the method according to the current safety guidelines (Iyer, 2005; Nitsche, 2003; Wassermann 2005) has little relevant side effects, including mild tingling sensation during or after stimulation, moderate fatigue, slight sensation of itching at the electrode application points, slight burning or pain, headache, nervousness, nausea, appearance of vesicles at the electrode application points in more rare cases.

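### The only adverse-event rule covers notification of events induced by an undefined method; no all-cause recording or by-arm comparison of harm is planned, although every patient also has TMS

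*Combined protocol and SAP*

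**What the plan says.** The section on detection of adverse events consists of one sentence: "The Principal Investigator will promptly communicate to the Provincial Ethics Committee of the Province of Brescia any adverse event induced by the method". It gives no schedule, checklist, severity grading or criteria for judging cause, and it does not say what *the method* is. In the risk-benefit section the term refers to tDCS when the tDCS side effects are introduced, and to TMS in the paragraphs just before the rule.

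The side effects listed for tDCS include "slight burning or pain, headache, nervousness, nausea, appearance of vesicles at the electrode application points in more rare cases", with tingling, itching and fatigue; no rates are given. For TMS the protocol says that "a certain number of subjects participating in TMS experiments (up to 20%) suffer headaches or back pain". It thinks muscle tension and a rigid posture the likely reason, and calls the effects temporary.

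Under Study design, each patient has "evaluation of CBI connectivity by transcranial magnetic stimulation at baseline (T0), after 2 weeks of treatment with tDCS (T1"), and again at three months (T2). This applies to both arms, allocated 1:1. An open phase follows in which all patients receive real stimulation.

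The three primary and five secondary outcome measures cover ataxia scales, cognition, cerebellar-brain inhibition and quality of life. The Statistical plan covers baseline comparability and effects on cognition, coordination and balance, and quality of life. Neither mentions harm.

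**The concern.** Cause is the entry condition for the only adverse-event report that the plan describes. That judgement is hard where two study procedures share a symptom and both are given to the same patient. Headache is on both lists, and pain overlaps loosely.

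Randomisation against sham offers a better route. Patients in both arms have the same TMS, so its background drops out of the difference between arms and nobody has to decide the cause of one headache. This works only if events are collected alike in both arms, whatever their presumed cause. The plan provides for neither the collection nor the comparison.

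The trial aims to identify a possible rehabilitation protocol, and its risk-benefit argument rests on published data. As written, it does not plan to add tolerability evidence of its own against sham. The comparison exists only from T0 to T2; what is not recorded by arm in that window cannot be rebuilt later.

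**Working it through.** The plan states no figure for harm by arm, so there is none to reproduce. Its calculated sample size of 54 concerns efficacy and does not enter here.

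**Inputs**
- Patients per arm at 1:1. Study design has "for 2 consecutive weeks in 40 patients with neurodegenerative ataxia", so 40/2 = 20. The Statistical plan has "The proposed sample size of 60 subjects should be adequate to achieve the main objective of the study", so 60/2 = 30. The two totals need reconciling as a separate matter; both are carried here.
- Headache or back pain with TMS: up to 20%, read as a proportion of participants. This is an upper limit, so 10% and 5% are shown as assumptions.
- Headache or pain from tDCS: no rate in the documents.

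**1. Background events expected per arm (n × rate)**

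| Rate | 20 per arm | 30 per arm |
|---|---|---|
| 20% (protocol's limit) | 4 | 6 |
| 10% (assumed) | 2 | 3 |
| 5% (assumed) | 1 | 1.5 |

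At 20%, the central 95% binomial range is 1 to 8 of 20, or 2 to 11 of 30. The chance of at least one such patient in an arm is 1 − 0.8^20 = 0.988, or 1 − 0.8^30 = 0.999.

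**2. Why the arm comparison removes the background**

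If TMS contributes a risk b in each arm and real stimulation adds d over sham, the expected difference is (b + d) − b = d. A patient-by-patient judgement has no such cancellation.

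**3. Precision of a by-arm table**

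With both arms at 20%, the half-width of the 95% interval for the risk difference is 1.96 × √(2 × 0.20 × 0.80 / n).
- n = 20: 1.96 × √0.016 = 0.248, about ±25 points.
- n = 30: 1.96 × √0.01067 = 0.202, about ±20 points.

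**4. Power if the comparison were tested**

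Assume 20% on sham and 40% on real stimulation, two-sided 5%. Power = Φ[(0.20 − 1.96 × √(2 × 0.30 × 0.70 / n)) / √((0.20 × 0.80 + 0.40 × 0.60) / n)].
- n = 20: Φ[(0.20 − 0.284)/0.1414] = Φ(−0.594) = 0.28; Fisher's exact test gives 0.19.
- n = 30: Φ[(0.20 − 0.232)/0.1155] = Φ(−0.276) = 0.39; Fisher's exact test gives 0.30.

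For 80% power at this assumed excess, 82 patients per arm would be needed. The comparison is therefore descriptive.

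**The case against.** The strongest reply is that the sentence is a notification rule. It does not bar the site from recording other events, and limiting prompt notification to related events is not in itself an error. This stands. A reader might infer that events judged unrelated are lost; the documents do not say so. They show only that no other collection rule is written down.

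Second, *the method* may cover both procedures. On that reading a headache from either is reportable, and notification does not require telling them apart. This also stands as far as notification goes. It does not supply a comparison of real with sham stimulation, and the term remains undefined.

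Third, attribution is not hopeless. TMS is given only at evaluation visits, its effects are called temporary, and itching or vesicles at the electrodes point to tDCS. The difficulty is confined to headache and pain, mainly near the visits that border the tDCS course. The Procedures section can also be read as placing the second evaluation two weeks after treatment ends; if so, the overlap at T1 is smaller, and the two descriptions of T1 should be reconciled.

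Three stronger readings are tempting but unsupported:
- *That the investigator who judges cause is blinded.* Study design blinds patients and those who administer the tests. It does not say whether the Principal Investigator is blinded.
- *That TMS-related events would outnumber those from tDCS.* With no tDCS rate this turns on assumptions. For an added risk of 10 or 20 points, the TMS share b/(b + d) in the real arm is 0.20/0.30 = 67% or 0.20/0.40 = 50% at a 20% background, but 0.05/0.15 = 33% or 0.05/0.25 = 20% at a 5% background.
- *That counts of tingling or itching by arm would show whether the sham felt like real stimulation.* They would be indirect evidence at most.

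**Conclusion.** The point holds as a gap in collection and comparison. One notification rule with an undefined scope is all the plan says about recording harm, and no outcome or analysis compares harm between arms. At the protocol's own upper limit, about 4 of 20 or 6 of 30 patients per arm would have headache or back pain with TMS, so single-patient attribution of those symptoms is uncertain around T0 and T1. The counts rest on reading 20% as a per-participant rate and shrink in proportion if the true rate is lower.

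No efficacy endpoint or efficacy analysis is affected. The change is worth making because it is cheap and because the sham-controlled window closes at T2. It would not give a powered safety test.

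**What to change.** - At each of the ten tDCS sessions and at every evaluation visit, record all adverse events in both arms regardless of presumed cause. Use the effects that the protocol already lists for tDCS and TMS as a fixed checklist, with presumed attribution as a separate field.
- Add to the Statistical plan a table of the proportion of patients with each event, real against sham, through T2, with risk differences and 95% confidence intervals. Label it descriptive.
- Keep the prompt report to the Ethics Committee, and state that *the method* covers both tDCS and TMS.

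The cost is a short checklist at sessions and visits already attended and one table. The downside is a few minutes per session and more minor events on record. No dose, schedule or treatment rule changes.
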